4.6 Blinding/Unblinding

Not applicable.

4.7 Treatment Compliance

Treatment compliance will be monitored by drug accountability as well as the subject's medical record and eCRF.

4.8 Destruction of Study Drug

For this study, study drugs (those supplied by BMS or sourced by the investigator) such as partially used study drug containers, vials and syringes may be destroyed on site.

Any unused study drugs can only be destroyed after being inspected and reconciled by the responsible Study Monitor unless study drug containers must be immediately destroyed as required for safety, or to meet local regulations (eg, cytotoxics or biologics).

On-site destruction is allowed provided the following minimal standards are met:

- On-site disposal practices must not expose humans to risks from the drug.
- On-site disposal practices and procedures are in agreement with applicable laws and regulations, including any special requirements for controlled or hazardous substances.
- Written procedures for on-site disposal are available and followed. The procedures must be filed with the site's SOPs and a copy provided to BMS upon request.
- Records are maintained that allow for traceability of each container, including the date disposed of, quantity disposed, and identification of the person disposing the containers. The method of disposal, ie, incinerator, licensed sanitary landfill, or licensed waste disposal vendor must be documented.
- Accountability and disposal records are complete, up-to-date, and available for the Monitor to review throughout the clinical trial period.

If conditions for destruction cannot be met the responsible Study Monitor will make arrangements for return of study drug.

It is the investigator's responsibility to arrange for disposal of all empty containers, provided that procedures for proper disposal have been established according to applicable federal, state, local, and institutional guidelines and procedures, and provided that appropriate records of disposal are kept.

4.9 Return of Study Drug

If study drug will not be destroyed upon completion or termination of the study, all unused and/or partially used study drug that was supplied by BMS must be returned to BMS. The return of study drug will be arranged by the responsible Study Monitor.

It is the investigator's responsibility to arrange for disposal of all empty containers, provided that procedures for proper disposal have been established according to applicable federal, state, local, and institutional guidelines and procedures, and provided that appropriate records of disposal are kept.

5 STUDY ASSESSMENTS AND PROCEDURES

5.1 Flow Chart/Time and Events Schedule

Table 5.1-1: Screening Procedural Outline (CA209401)

Procedure	Screening Visit ^a	Notes
Eligibility Assessments		
Informed Consent	X	
Inclusion/Exclusion Criteria	X	Assessed at screening visit prior to any procedures and reassessed prior to first dose.
Medical History	X	Documentation of mutation status (BRAF, NRAS, cKIT) if considered standard of care or if otherwise known.
Safety Assessments		
Physical Examination	X	Included height, weight, ECOG PS. Focused physical exam performed at screening, if clinically indicated.
ECOG Performance Status	X	ECOG PS 0-1 ECOG PS 2
Vital Signs and Oxygen Saturation	X	Temperature, BP, RR, O2 saturation by pulse oxymetry at rest (also monitor amount of supplement oxygen if applicable). Obtain vital signs at screening visit and within 72 hours of first dose.
Serious Adverse Events Assessment	X	
Adverse Events Assessment	X	No AE collection before first dose.
Assessment of Signs and Symptoms	X	After obtaining Informed Consent, assess all signs and symptoms within 14 days of first dose, prior to study treatment initiation.
Laboratory Tests	X	Chemistry tests performed locally within 14 days prior to first dose (unless otherwise specified): CBC with differential, chemistry (BUN or serum urea level, creatinine, sodium, potassium, calcium, magnesium, phosphate, chloride, and glucose), AST, ALT, total bilirubin, alkaline phosphatase, albumin, LDH, TSH, free T3, free T4, and lipase. Within 28 days prior to first dose, hepatitis B surface

Table 5.1-1: Screening Procedural Outline (CA209401)

Procedure	Screening Visit ^a	Notes
		antigen (HBsAg) and hepatitis antibody (HCV Ab).
Pregnancy Tests	X	Performed within 24 hours prior to first dose for WOCBP only (serum or urine as required by the standard of care at the site). An extension of up to 72 hours prior to the first dose of nivolumab and ipilimumab is permissible in situations where results cannot be obtained within the standard 24 hour window. See Section 3.3.3 for the definition of Women of Childbearing Potential
Tumor Tissue Sample	X	May be archival. 1 paraffin block or a minimum of 10 FFPE unstained slides received by Central Lab prior to subject enrollment. (FNA and bone metastases samples not acceptable)
Additional Assessments		
[REDACTED]		
Efficacy Assessments		
Screening/Baseline Tumor Assessments	X	Chest, abdomen, pelvis, brain, and other known sites of disease within 6 weeks of the first dose of study therapy. Subjects must have evaluable disease by CT or MRI per RECIST 1.1 criteria (radiographic tumor assessment performed within 6 weeks prior to first dose of study) or clinically apparent disease that the investigator to follow for response.

ALT, alanine aminotransferase; AST, aspartate aminotransferase; BP, blood pressure; BUN, blood urea nitrogen; CBC, complete blood count; CT, computerized tomography; ECOG, Eastern Cooperative Oncology Group; EORTC QLQ-C30, European Organization for Research and Treatment of Cancer Quality of Life Questionnaire; HBsAg, hepatitis B surface antigen; HCV Ab, hepatitis C antibody; LDH, lactate dehydrogenase; MRI, magnetic resonance imaging; O2, oxygen; PS, Performance Status; RECIST, Response Evaluation Criteria in Solid Tumors; RR, respiratory rate; TSH, thyroid stimulating hormone; WOCBP, women of child bearing potential

^a Within 28 days ± 5 days before start of nivolumab and ipilimumab combination regimen

Table 5.1-2: On Study Assessments Part I: Cycles 1 Through 4 (Nivolumab Plus Ipilimumab)^a

Procedure	Every Cycle (Every 3 weeks)	Every 2 Cycles (Every 6 Weeks)	Notes
Safety Assessments			
Physical Measurements (including PS)	X		Collect weight and ECOG PS within 72 hours prior to dosing. Focused physical exams should be performed as clinically indicated.
Vital Signs and Oxygen Saturation	X		Tests include temperature, BP, HR, RR, O2 saturation by pulse oxymetry at rest (also monitor amount of supplemental oxygen if applicable) within 72 hours prior to dosing and at any time a subject has any new or worsening respiratory symptoms
Serious Adverse Event Assessments	---	---See notes---	Assessments are done during office visits and by weekly calls to subject during weeks the subject is not in the office for a clinic visit. Assessed using NCI CTCAE v 4.0. See Appendix 1 .
Adverse Event Assessment	---	---See notes---	Assessments are done during office visits and by weekly calls to subject during weeks the subject is not in the office for a clinic visit. Assessed using NCI CTCAE v 4.0.
			
Laboratory Tests: CBC with differential	X		CBCs with differential includes white blood cell count, lymphocyte count, absolute neutrophil count, hemoglobin, hematocrit, and platelet count. Laboratory tests should be completed and reviewed within 72 hours prior to dosing on infusion days.
Laboratory Test: Chemistry test	X		Chemistry tests include BUN or serum urea level, creatinine, sodium, potassium, calcium, chloride, amylase, lipase, glucose, phosphate, LDH, and magnesium.
Laboratory Test: Liver function tests	X		Liver function tests include AST, ALT, total bilirubin, alkaline phosphatase, albumin.
Laboratory Tests: Thyroid function tests		X	Thyroid function testing including TSH (free T3 and free T4 if abnormal results for TSH)
Pregnancy Test	X		Completed more frequently if required by local regulations (serum or blood as required by standard of care at the site). Pregnancy testing may be performed at home if an in-office visit is otherwise not required.

Table 5.1-2: On Study Assessments Part I: Cycles 1 Through 4 (Nivolumab Plus Ipilimumab)^a

Procedure	Every Cycle (Every 3 weeks)	Every 2 Cycles (Every 6 Weeks)	Notes
Efficacy Assessments			
Tumor Scans	---	---See notes---	Initial tumor assessment, utilizing RECIST 1.1 criteria, is to be completed at Week 12 (±5 days). Further tumor assessments are recommended to be completed as required by local standards of care or at the investigator discretion and are recommended every 8 weeks.
Outcomes Assessments			
[REDACTED]			
Clinical Drug Supplies			
Administration of Study Drug	X		

^a If a dose is delayed, the procedures scheduled for that same time point should also be delayed to coincide with when that time point’s dosing actually occurs. ALT, alanine aminotransferase; AST, aspartate aminotransferase; BP, blood pressure; BUN, blood urea nitrogen; CBC, complete blood count; ECOG, Eastern Cooperative Oncology Group; EORTC QLQ-C30, European Organization for Research and Treatment of Cancer Quality of Life Questionnaire; HR, heart rate; LDH, lactate dehydrogenase; LFT, liver function test; NCI CTCAE, National Cancer Institute Common Terminology Criteria for AEs; O2, oxygen; PS, Performance Status; NCI CTACE, National Cancer Institute Common Terminology Criteria for Adverse Events; RECIST, Response Evaluation Criteria in Solid Tumors; RR, respiratory rate; TSH, thyroid stimulating hormone; TFT, thyroid function test.

Table 5.1-3: On-Treatment Assessments Part II: Cycles 5 and Beyond (Nivolumab Monotherapy)^{a,b}

Procedure	Every Cycle (Every 2 weeks)	Every 2 Cycles (Every 4 weeks)	Every 3 Cycles (Every 6 weeks)	Every 4 Cycles (Every 8 weeks)	Notes
Safety Assessments					
Physical Measurements (including PS)	X				Collect weight and ECOG PS within 72 hours and review prior to dosing. Focused physical exams should be performed as clinically indicated.
Vital Signs and Oxygen Saturation	X				Tests include temperature, BP, HR, RR, O2 saturation by pulse oxymetry at rest (also monitor amount of supplemental oxygen if applicable) within 72 hours prior to dosing and at any time a subject has any new or worsening respiratory symptoms.
Serious Adverse Event Assessments	X				Assessed using NCI CTCAE v 4.0. See Appendix 1 .
Adverse Event Assessment	X				Assessed using NCI CTCAE v 4.0
					
Laboratory Tests: CBC with differential	X				As required by local standard of care or at the investigator's discretion. Includes white blood cell count, lymphocyte count, absolute neutrophil count, hemoglobin, hematocrit, and platelet count.
Laboratory Tests: Chemistry test	X				Includes blood urea nitrogen [BUN] or serum urea level, creatinine, sodium, potassium, calcium, chloride, amylase, lipase, glucose, phosphate, LDH, and magnesium
Laboratory Tests: Liver function test	X				Includes AST, ALT, total bilirubin, alkaline phosphatase, albumin.

Table 5.1-3: On-Treatment Assessments Part II: Cycles 5 and Beyond (Nivolumab Monotherapy)^{a,b}

Procedure	Every Cycle (Every 2 weeks)	Every 2 Cycles (Every 4 weeks)	Every 3 Cycles (Every 6 weeks)	Every 4 Cycles (Every 8 weeks)	Notes
Laboratory Test: Thyroid function test			X		Includes TSH (free T3 and free T4 if abnormal results for TSH)
Pregnancy Test		X			Completed more frequently if required by local regulations (serum or blood as required by standard of care at the site). Pregnancy testing may be performed at home if an in-office visit is otherwise not required.
Efficacy Assessments					
Tumor Scans		---See notes---			Recommended to be completed as required by local standards of care or at the investigator's discretion and are recommended every 8 weeks. Subjects with brain metastasis should have surveillance MRI approximately every 12 weeks or sooner if clinically indicated.
Outcomes Assessments					

Table 5.1-3: On-Treatment Assessments Part II: Cycles 5 and Beyond (Nivolumab Monotherapy)^{a,b}

Procedure	Every Cycle (Every 2 weeks)	Every 2 Cycles (Every 4 weeks)	Every 3 Cycles (Every 6 weeks)	Every 4 Cycles (Every 8 weeks)	Notes
Clinical Drug Supplies					
Administration of Study Drug	X				

ALT, alanine aminotransferase; AST, aspartate aminotransferase; BP, blood pressure; BUN, blood urea nitrogen; CBC, complete blood count; ECOG, Eastern Cooperative Oncology Group; EORTC QLQ-C30, European Organization for Research and Treatment of Cancer Quality of Life Questionnaire; HR, heart rate; LDH, lactate dehydrogenase; LFT, liver function test; NCI CTCAE, National Cancer Institute Common Terminology Criteria for AEs; O2, oxygen; PS, Performance Status; NCI CTACE, National Cancer Institute Common Terminology Criteria for Adverse Events; RECIST, Response Evaluation Criteria in Solid Tumors; RR, respiratory rate; TSH, thyroid stimulating hormone; TFT, thyroid function test.

^a If a dose is delayed, the procedures scheduled for that same time point should also be delayed to coincide with when that time point's dosing actually occurs.

^b Cycle 5 begins 3 weeks after Cycle 4.

Table 5.1-4: Follow Up Assessments for Subjects who Discontinue in Part I^a

Procedure	Every 4 Weeks (± 7 days) through 100 Days after last dose of study drug	Notes
Safety Assessments		
Physical Exams	X	Collect weight and ECOG PS. Focused physical examination may be performed if clinically indicated and to assess for potential late emergent study drug related issues.
Vital signs and Oxygen Saturation	X	Temperature, BP, HR, RR, O2 saturation by pulse oximetry at rest (also monitor amount of supplemental oxygen if applicable) at any time a subject has any new or worsening respiratory symptoms.
		
Adverse Event Assessment	X	All nonserious AEs (not only those deemed to be treatment-related) should be collected continuously during the treatment period and for a minimum of 100 days following the last dose of study treatment. Nonserious AEs should be followed to resolution to stabilization or reported as SAEs if they become serious.
Serious Adverse Event Assessments	X	All SAEs that occur during the screening period and within 100 days of discontinuation of dosing must be collected.
Laboratory Tests: CBC with differential	X	Includes WBC, lymphocytes, ANC, hemoglobin, hematocrit, platelet count.
Laboratory Tests: chemistry tests	X	Includes BUN or serum urea, creatinine, sodium, potassium, calcium, magnesium, phosphate, chloride, glucose, amylase, lipase, and LDH.
Laboratory Tests: Liver function tests	X	Includes AST, ALT, total bilirubin, alkaline phosphate, albumin
Efficacy Assessments		
Subject survival status	---see notes---	May be accomplished by visit for the first 100 days and then by visit or phone for up to 2 years from the first dose of combination regimen therapy
Laboratory Tests: Thyroid function tests	X	Includes TSH (reflect to free T3 and free T4 if abnormal results)
Tumor scans	---see notes---	Tumor progression scans are recommended to be completed as required by local standards of care or at the investigator's discretion for up to 2 years.

Table 5.1-4: Follow Up Assessments for Subjects who Discontinue in Part I^a

Procedure	Every 4 Weeks (± 7 days) through 100 Days after last dose of study drug	Notes
Pregnancy Test in WOCBP	X	Completed more frequently if required by local regulations (serum or blood as required by standard of care at the site). Pregnancy testing may be performed at home if an in-office visit is otherwise not required.
Outcomes Assessments		
[REDACTED]	[REDACTED]	[REDACTED]

^a Subjects who discontinue in Part I are recommended to be followed by direct contact (office visit) every 4 weeks (± 7 days) for up to 100 days from the last dose or should coincide with the date of discontinuation (± 7 days) if the date of discontinuation is greater than 4 weeks (± 7 days) after the last dose. Beyond 100 days from the last dose of study therapy, subjects will be followed for ongoing drug-related AEs until resolved, AE symptoms return to baseline, or are deemed irreversible, for up to 2 years from the first dose or until lost to follow-up, withdrawal of study consent, or death, whichever comes first.

Table 5.1-5: Follow Up Assessments for Subjects who Discontinue in Part II

Procedure	FU-X01 (30 days ±7 days)	FU-X02 (70-84 days after FU-X01 ±7 days)	Follow-Up Visits after FU-X02. Every 24 weeks ±2 weeks	Notes
Safety Assessments				
Physical Examination	X	X		Collect weight and ECOG PS. Focused physical examination may be performed if clinically indicated and to assess for potential late emergent study drug related issues.
Vital signs and Oxygen Saturation	X	X		Temperature, BP, HR, RR, O2 saturation by pulse oximetry at rest (also monitor amount of supplemental oxygen if applicable) at any time a subject has any new or worsening respiratory symptoms.
	■	■		
AEs Assessment	X	X	X	All nonserious AEs (not only those deemed to be treatment-related) should be collected continuously during the treatment period and for a minimum of 100 days following the last dose of study treatment. Nonserious AEs should be followed to resolution to stabilization or reported as SAEs if they become serious.
Serious Adverse Events Assessments	X	X	X	All SAEs must be collected that occur during the screening period and within 100 days of discontinuation of dosing.
Laboratory Tests: CBC with differential	X	X		Includes WBC, lymphocytes, ANC, hemoglobin, hematocrit, platelet count.
Laboratory Tests: Chemistry tests	X	X		Includes BUN or serum urea, creatinine, sodium, potassium, calcium, magnesium, phosphate, chloride, glucose, amylase, lipase, and LDH.
Laboratory Tests: Liver function tests	X	X		Includes AST, ALT, total bilirubin, alkaline phosphatase, albumin.

Table 5.1-5: Follow Up Assessments for Subjects who Discontinue in Part II

Procedure	FU-X01 (30 days ±7 days)	FU-X02 (70-84 days after FU-X01 ±7 days)	Follow-Up Visits after FU-X02. Every 24 weeks ±2 weeks	Notes
Laboratory Tests: Thyroid function tests	X	X		Includes TSH (reflect to free T3 and free T4 if abnormal results)
Pregnancy Test in WOCBP	X	X		Completed more frequently if required by local regulations (serum or blood as required by standard of care at the site). Pregnancy testing may be performed at home if an in-office visit is otherwise not required.
Efficacy Assessments				
Tumor Scans		---See Notes---		Tumor progression scans are recommended to be completed as required by local standards of care or at the investigator’s discretion for up to 2 years.
Subject Survival Status	X	X	X	The first 2 visits are to be accomplished by onsite visit and then by visit or phone for up to 2 years from the first dose of combination regimen therapy.
Outcomes Assessments				

ANC, absolute neutrophil count; BP, blood pressure; CBC: complete blood count; WBC, white blood cells. Follow up period begins when the decision to discontinue a patient from study therapy is made (no further treatment with nivolumab) and continues from first dose of study therapy up to 2 years (+ 100 days following the last dose of study treatment) or until death, withdrawal of study consent, or lost-to-follow-up, whichever comes first.

Follow-up visit 1 (FU1) = 30 days from the last dose ±7 days or coincide with the date of discontinuation (± 7 days) if date of discontinuation is greater than 37 days after last dose, Follow-up visit 2 (FU2) = 84 days (± 7 days) from follow-up visit 1. Follow up visits 1 and 2 will occur within 100 days of last dose only after subject completes all study treatment. Beyond 100 days from the last dose of study therapy, subjects will be followed for ongoing drug-related AEs until resolved, AE symptoms returned to baseline, or are deemed irreversible, until lost to follow-up, or withdrawal of study consent or death.

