For Part I, nivolumab and ipilimumab are administered every 3 weeks for 4 doses (Table 5.1-2). If subjects discontinue therapy during Part I, nivolumab monotherapy can be continued as

described in [Section 4.5.5](#). **For Part II**, nivolumab monotherapy is administered every 2 weeks ([Table 5.1-3](#)) until 24 months after the first combination dose (Part I and II). Subjects may be treated for more than 24 months for a maximum of 50 cycles in case an on-hold period occurs during the Treatment Phase.

Windows for dosing of both Part I and Part II are discussed in [Section 4.5](#).

An initial tumor assessment is to be completed at Week 12 (± 5 days) after the first treatment dose. Further tumor assessments are recommended to be completed as required by local standards of care or at the investigator's discretion and are recommended every 8 weeks until documented tumor progression.

Subjects treated with the study drugs will be permitted to continue treatment beyond initial PD as assessed by the investigator's clinical judgment and local standards of care as long as they meet the criteria specified in [Section 4.5.8](#).

The Treatment Phase ends when the subject is discontinued from study therapy. For a complete list of reasons for treatment discontinuation, see [Sections 3.5](#) and [4.5.6](#).

The Follow-up Phase begins when the decision to discontinue a subject from study therapy is made (no further treatment with study therapy) ([Table 5.1-4](#) and [Table 5.1-5](#)):

- Subjects who discontinue therapy in Part I are recommended to be followed by direct contact (office visit) every 4 weeks for up to 100 days after the last dose of combination regimen therapy. After completion of the onsite follow-up visits (for up to 100 days), subjects will be followed every 24 weeks ± 2 weeks for survival either by direct visit or via telephone contact. OS will be followed from the start of therapy up to 2 years or until death, withdrawal of study consent, or lost-to-follow-up, whichever comes first.

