- For subjects who complete or discontinue therapy in Part II, subjects will have 2 follow-up visits (office visits): one approximately 30 days after the last dose of study drug and one approximately 100 days after the last dose of study drug. After completion of the first 2 follow-up visits, subjects will be followed every 24 weeks ± 2 weeks for survival either by phone contact or direct contact. OS will be followed in accordance with [Table 5.1-4](#) and [Table 5.1-5](#) from the start of therapy up to 2 years (+ 100 days following the last dose of study treatment), or until death, withdrawal of study consent, or lost-to-follow-up, whichever comes first.
- For subjects who complete therapy in Part II (2 years of treatment), subjects will have 2 follow-up visits (office visits): one approximately 30 days after the last dose of study drug and one approximately 100 days after the last dose of study drug.

Subjects who discontinue treatment for reasons other than tumor progression will continue to have tumor assessments according to the local standards of care and in accordance with [Table 5.1-4](#) and [Table 5.1-5](#).

Subjects will be followed for drug-related toxicities until these toxicities resolve, return to baseline, are deemed irreversible, lost to follow up, or withdrawal of study consent. All AEs will

be documented for a minimum of 100 days after last dose. Additional details regarding the follow up are discussed in [Section 5.3](#), [Table 5.1-4](#), and [Table 5.1-5](#).

The study design schematic is presented in Figure 3.1-1.

Figure 3.1-1: Study Design Schematic

Study Population	Treatment	Duration of Treatment

 • Unresectable or metastatic melanoma • First-line subjects for advanced disease 	
Part I: nivolumab 1 mg/kg IV + ipilimumab 3 mg/kg IV every 3 weeks X 4
 
Part II: nivolumab 3 mg/kg or 240 mg^a IV every 2 weeks until progression or a maximum of 24 months from the first combination dose (Part I and Part II) whichever comes first.
	
Part I: treat for 12 weeks (4 doses)
 
Part II: treat for a maximum of 24 months^b from first combination dose (Part I and Part II) until progression^c or unacceptable toxicity.

Part I (3 months) + Part II (up to 21 months) = maximum of 24 months

- ^a Sites who begin enrollment after the implementation of Amendment 04 will administer 240 mg IV instead of 3 mg/kg.

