In order to derive the time-to resolution, overlapping or contiguous select AEs within a specific category (defined in Table A-2) will be collapsed into what will be termed “clustered” select AEs. For example, if a subject (without pre-treatment AE) experienced an AE from 1st to 5th January, another AE (with different PT but within same category) from 6th to 11th January and same AE from 10th to 12th January, these will be collapsed into one clustered select AE from 1st to 12th January. Table A-1 is summarizing key derivation steps for each type of clustered select AEs.

Time-to resolution of select AE (any grade) for a specific category is defined as the longest time from onset to complete resolution or improvement to the grade at baseline among all clustered select AEs in this category experienced by the subject. Events which worsened into grade 5

events (death) or have a resolution date equal to the date of death are considered unresolved. If a clustered select AE is considered as unresolved, the resolution date will be censored to the last known date alive. Improvement to the grade at baseline implies that all different AE events in the clustered select adverse event should at least have improved to the corresponding (i.e. with same preferred term) baseline grade. This measure is defined only for subjects who experienced at least one select AE in the specific category.

The time-to resolution of select AE (grade 3-5) for a specific category is defined similarly with an onset date corresponding to a grade 3-5 select AE.

Time-to resolution of drug-related select AE (any grade or grade 3-5) is defined similarly but restricted to drug-related select AE.

The time-to resolution of select AE (any grade or grade 3-5, drug-related or all) where immune modulating medication was initiated is defined similarly with the additional condition that the subject started an immune modulating medication during the longest select AE resolution period.

Time-to resolution for a specific subcategory is defined similarly but restricted to event of this subcategory.

Table A-1: Derivation of clustered select AE

Type of clustered select AE	Derivation
Any grade	Collapse any on-treatment select AE from the same category
Drug-related of any grade	Collapse any on-treatment drug-related select AE from the same category

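### Table 5.1-4 schedules no contact for the post-100-day AE follow-up that its own footnote requires, while the SAP keeps unresolved select AEs at risk to the last date known alive; if late resolutions go unrecorded, time to resolution is biased upward

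*Protocol*

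**What the plan says.** **Visit grid.** The single column of Protocol Table 5.1-4 reads "Every 4 Weeks (± 7 days) through 100 Days after last dose of study drug". Its AE row asks for collection "for a minimum of 100 days following the last dose of study treatment", which is a floor and not a stopping point.

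**Later AE follow-up.** Footnote a of that table says: "Beyond 100 days from the last dose of study therapy, subjects will be followed for ongoing drug-related AEs until resolved". Its other end points include "deemed irreversible, for up to 2 years from the first dose or until lost to follow-up". Section 3.1 sets a similar duty: "Subjects will be followed for drug-related toxicities until these toxicities resolve, return to baseline, are deemed irreversible". Neither place gives an interval or a visit.

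**Later contacts.** For these subjects Section 3.1 says that after the onsite visits "subjects will be followed every 24 weeks ± 2 weeks for survival either by direct visit or via telephone contact".

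**The sister table.** Table 5.1-5, for subjects who stop in Part II, has a column headed "Follow-Up Visits after FU-X02. Every 24 weeks ±2 weeks". Its AE and SAE rows are marked there.

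**Events of any causality.** Sections 6.1.1 and 6.2.1 allow follow-up to end at resolution or at stabilization.

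**Analysis.** SAP Appendix 1 counts an event as resolved on complete resolution or return to the baseline grade. It then says: "If a clustered select AE is considered as unresolved, the resolution date will be censored to the last known date alive".

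**The concern.** Knowing that a subject is alive is not the same as knowing the state of an AE. Censoring at the last date known alive is sound only if a resolution before that date would have been recorded. For Part I discontinuers the protocol sets a duty to follow drug-related events but schedules no contact at which to do it. For unrelated select AEs, follow-up may properly end at stabilization, which is not resolution as the SAP defines it. The subject still stays at risk in the analysis.

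The outcome of high-grade select AEs, including time to resolution, is the first secondary objective, and it is not limited to related events. Subjects who stop during Part I for toxicity matter most to it. If late resolutions are missed, toxicity looks less reversible than it is. Part I and Part II discontinuers would also be measured differently.

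**Working it through.** The documents give no figure for time to resolution, so there is none to reproduce. Steps 1 to 3 use document inputs; steps 4 and 5 are illustrations on assumed inputs.

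**1. Last visit on the grid.** Visit k falls at 28k ± 7 days after last dose: Days 21–35, 49–63, 77–91 and 105–119. The fourth cannot occur by Day 100, so the last is nominally Day 84.

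**2. Time left at risk.** With d doses given 21 days apart, Day 84 after last dose is day 21(d − 1) + 84 from first dose: 84, 105, 126 or 147 for d = 1 to 4. Up to 2 years (730 days) that leaves 646, 625, 604 or 583 days.

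**3. What covers that time.**

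| Select AE open at Day 100 | Duty to follow | AE contact in Table 5.1-4 | SAP censoring |
|---|---|---|---|
| Drug-related | Footnote a, Section 3.1: to an outcome | none | last date known alive |
| Not related | Sections 6.1.1 and 6.2.1: resolution or stabilization | none | last date known alive |

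**4. Size if late resolutions are missed.** Assumptions: onset uniform from Day −30 to Day 60 relative to last dose; exponential resolution with median m; complete recording to Day 84; a share c of subjects with complete recording afterwards; all known alive to at least Day 300. Everyone is then followed for at least 300 − 60 = 240 days from onset, so the Kaplan-Meier value at 180 days under the SAP rule is simply the share with a recorded resolution.

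Let X = 84 − onset, uniform on 24 to 114 days, and λ = ln 2 / m. With c = 0:

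- Share unresolved at 180 days = [exp(−24λ) − exp(−114λ)] / (90λ).
- For t between 24 and 114, G(t) = [exp(−24λ) − exp(−λt)] / (90λ) + exp(−λt)(114 − t)/90. The observed median solves G(t) = 0.5.

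For m = 60: (0.758 − 0.268)/1.040 = 0.471 unresolved, so 52.9% resolved against a true 1 − 2⁻³ = 87.5%. G(78) = 0.338 + 0.162 = 0.501, so the median is about 78 days.

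For c = 0.5: (52.9 + 87.5)/2 = 70.2% resolved. At t = 65, ½(0.472) + ½(0.532) = 0.502, so the median is about 65 days.

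| True median | Capture after Day 84 | Median, SAP rule | Resolved at 180 days | True |
|---|---|---|---|---|
| 60 | none | about 78 | 53% | 88% |
| 60 | half | about 65 | 70% | 88% |
| 60 | full | 60 | 88% | 88% |
| 30 | none | 30 | 76% | 98% |
| 120 | none | not reached | 32% | 65% |

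Row 4: (0.574 − 0.072)/2.079 = 0.242 unresolved, and G(30) = 0.036 + 0.467 = 0.502. Row 5: (0.871 − 0.518)/0.520 = 0.679 unresolved.

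With earlier onset (Day −14 to 28, so X runs from 56 to 98) and m = 60, the median stays at 60, since G(60) = 0.049 + 0.452 = 0.501. The 180-day figure is still (0.524 − 0.322)/0.485 = 0.415 unresolved, or 58.5% resolved. An unchanged median therefore does not clear the curve.

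**5. Would censoring every open event at the last AE assessment be better?** Not without an exception. Suppose 30% of events are irreversible and closed at Day 84, the rest have a 60-day median, and all resolutions are captured. The true 180-day figure is 0.7 × 0.875 = 61%, and the true median is 60 × log₂(0.7/0.2) = 108 days. The SAP rule returns both. In simulation, censoring every open event at its last assessment gives 81–82% and 90 days, which errs the other way.

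**The case against.** The strongest reply is that the protocol already requires the follow-up. Footnote a and Section 3.1 cover drug-related events. Section 5.3 ends safety assessments at about 100 days only provided AEs have resolved, and adds weekly AE calls in weeks without visits. Sections 6.1.1 and 6.2.1 cover events of any causality. Footnote a's 2-year limit is also the survival limit for the same subjects, so the SAP's censoring horizon matches the protocol's. Events deemed irreversible are truly unresolved, and carrying them forward is correct. Subjects who go on to monotherapy under Section 4.5.5 would come under Table 5.1-5 when they stop, which narrows the affected group; the documents do not say how many remain.

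Most of this stands. A reader might infer that AE follow-up ends at Day 84, or that time to resolution is necessarily overstated. The documents support neither: full capture gives zero bias. The weekly calls also make a separate Day-100 call largely redundant.

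What the reply does not meet is narrower. The duty has no scheduled contact in Table 5.1-4 although Table 5.1-5 has one. Unrelated events may be closed at stabilization. The SAP does not distinguish event status known from subject known alive.

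**Conclusion.** The concern holds as a conditional risk. The schedule gap and the difference between the two tables are facts of the documents. The bias arises only for resolutions after the last recorded AE status, chiefly slow or late-onset events and select AEs judged unrelated. Its direction is then known: time to resolution too long, proportion resolved too low.

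In the 60-day illustration the 180-day proportion falls by about 35 percentage points with no late capture (87.5 − 52.9) and about 17 with half (87.5 − 70.2). A 30-day median is essentially unaffected, although its 180-day proportion is not. Onset, resolution and capture rates are all assumptions. The Core Safety SAP, to which SAP Section 7.6.2.2 refers for time to onset and resolution, is not available and may add conventions.

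**What to change.** **Protocol.** Add to Table 5.1-4 the 24-week column of Table 5.1-5, and mark AE and SAE there. At the existing survival contact, ask for the status and end date of any select AE still open, related or not. No extra Day-100 call is needed.

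**SAP Appendix 1.** Keep the current rule as primary. Add a sensitivity analysis that censors unresolved select AEs in living subjects at the last date AE status was assessed. Keep events deemed irreversible as unresolved to the last date known alive. The data must therefore hold the last AE status date and identify events deemed irreversible.

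Both parts are needed. If nothing is recorded after Day 84, no event in the illustration is observed beyond 84 + 30 = 114 days from onset, and censoring alone cannot recover what happens later.

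**Cost.** One table column, a few questions at contacts already planned, and one added SAP analysis. Survival contacts become slightly longer, and end dates may be recalled over as much as 24 weeks.
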